3.6.2.1 Asthma symptom score

Asthma symptoms during night-time and daytime will be recorded by the participant each morning and evening in the asthma daily diary. Each symptom item will be recorded using a scale 0 – 3, where 0 indicates no asthma symptoms. Asthma symptom daytime score (recorded in the evening), night-time score (recorded in the morning), and total score will be calculated and presented separately.

The daily asthma symptom total score will be calculated by taking the sum of the daytime and night-time asthma symptom scores recorded each day. If a participant is missing a value for

either night-time or daytime asthma symptom score on a given day, then the total score for that day will be set to missing.

The outcome variable is the change from baseline through Week 24 in 2-weekly mean daily asthma symptom total score. 2-weekly means and change from baseline for daytime and night-time scores will also be calculated for the 2-weekly periods according to Table 1 (Section 3.1.4).

3.6.2.2 Rescue medication usage

During the study period, participants will be required to document rescue medication usage in the eDiary twice daily. Daytime use is recorded in the evening and night-time use is recorded in the morning.

The outcome variable is the 2-weekly mean daily rescue medication usage (puffs/day) and will be calculated for the 2-weekly periods according to Table 1 (Section 3.1.4).

3.6.2.3 Nights with awakening due to asthma

Bi-weekly mean change from baseline in the number (percentage) of nights with awakening due to asthma that required rescue medication will be calculated as the outcome variable for the 2-weekly periods according to Table 1 (Section 3.1.4).

3.6.2.4 Home FEV₁

Bi-weekly mean absolute changes from baseline home FEV₁ will be calculated for the 2-weekly periods according to Table 1 (Section 3.1.4).

3.6.2.5 Home peak expiratory flow (morning and evening)

Bi-weekly mean absolute changes from baseline PEF will be calculated for the 2-weekly periods according to Table 1 (Section 3.1.4).

3.6.3 FEV₁% reversibility and FEF25-75%

Exploratory variables are the FEV₁% reversibility and FEF25-75%. They will be measured by in-clinic spirometry at visits SV1, SV2, SV4, SV8 and SV10. Reversibility is calculated as follows:

$$\text{FEV}_1\% \text{ reversibility} = (\text{post-BD FEV}_1 - \text{pre-BD FEV}_1) / \text{pre-BD FEV}_1 \times 100$$

The exploratory endpoint is the change from baseline to Weeks 8 and 16 in FEV₁% reversibility and FEF25-75%.

3.6.4 Asthma exacerbation

Asthma exacerbation will be assessed throughout the duration of the study.

Time to first asthma exacerbation will be calculated as start date of asthma exacerbation minus date of 1st dose plus 1.

The annualised rate of asthma exacerbation during intervention period (Baseline to last dose date +28 days) per participant will be calculated as:

Annualised exacerbation rate during intervention period =

$$\frac{\text{No. of exacerbations}}{(\text{Date of last dose of IP} + 28 - \text{Date of 1st dose} - \text{recovery time} + 1) / 365.25}$$

The annualised rate of hospitalised asthma exacerbation during intervention period per participant will be calculated as:

Annualised hospitalised exacerbation rate during intervention period =

$$\frac{\text{No. of exacerbations which resulted in hospitalisation}}{(\text{Date of last dose of IP} + 28 - \text{Date of 1st dose} - \text{recovery time} + 1) / 365.25}$$

The recovery time is defined as:

$$\sum_{i=1}^k [\min(i^{\text{th}} \text{ exacerbation end date} + 7, \text{date of last dose of study intervention} + 28) - i^{\text{th}} \text{ exacerbation start date} + 1]$$

3.6.5 Patient Global Impression of Benefit/Risk (PGI-BR)

The PGI-BR is a 5-item questionnaire assessing the participant's perception of the overall benefits and risks of treatment at SV10. The 5 items assess: overall trial experience, efficacy, side effects, convenience and overall assessment of the benefits and harms of treatment. Items are rated on 5- or 6-point verbal rating scales.

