ACQ-6 = asthma control questionnaire-6; AE = adverse event; BD = bronchodilator; COVID-19 = coronavirus disease 2019; CRS = chronic rhinosinusitis; E/D = early study intervention discontinuation; ECG = electrocardiogram; EDN = eosinophil derived neurotoxin; FeNO = fractional exhaled nitric oxide; IgE = immunoglobulin E; IL = interleukin; mRNA = messenger RNA; NT-proBNP = N-terminal prohormone of B-type natriuretic peptide; PGI-BR = patient global impression of benefit/risk; PK = pharmacokinetic(s); SAE = serious adverse event; SARS-CoV-2 = severe acute respiratory syndrome coronavirus 2; SGRQ = St George’s respiratory questionnaire; SNOT-22 = sino-nasal outcome test-22; CCI SOC = standard of care; sST2 = soluble ST2; SV = study visit; TC = telephone contact; VAS = visual analogue scale.

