To assess the longitudinal effect of MEDI3506 compared with placebo on lung function in adult participants with uncontrolled moderate-to-severe asthma.	As measured in clinic, change from baseline in pre-BD FEV1 to Weeks 1, 4, 8, 12, 20, and 24.
To assess the acute effect of MEDI3506 compared with placebo on pre-BD FEV1 in adult participants with uncontrolled moderate-to-severe asthma.	As measured in clinic, change in pre-BD FEV1 (L) from pre-administration of study intervention to 4 hours post-administration of MEDI3506 or placebo at Day 1.
To assess the effect of MEDI3506 compared with placebo on asthma control in adult participants with uncontrolled moderate-to-severe asthma.	During the intervention period (baseline to Week 16): 
 • Annualised rate of asthma exacerbations. • Annualised rate of hospitalised asthma exacerbations.
To assess the longitudinal effect of MEDI3506 compared with placebo on asthma control and health status in adult participants with uncontrolled moderate-to-severe asthma.	Change from baseline to Weeks 1, 4, 8, 12, and 24 in ACQ-6 score. Change from baseline to Weeks 4, 12, and 24 in SGRQ score. Change from baseline up to Week 24 in 2-weekly mean daily rescue medication usage (puffs/day). Change from baseline to Weeks 4, 8, 12, 16, 20, and 24 in: 
 • Asthma symptom score. • Mean number of night-time awakenings.
To assess the benefit-risk profile of MEDI3506 as perceived by adult participants with uncontrolled moderate-to-severe asthma.	PGI-BR at Week 16.
To evaluate CCI and inflammatory blood biomarkers that may predict an efficacy response to MEDI3506 in adult participants with uncontrolled moderate-to-severe asthma.	CCI  Association of allergen-specific IgE status with primary and secondary efficacy endpoints at Week 16.
To assess the effect of MEDI3506 compared with placebo on asthma related inflammatory airway biomarkers in adult participants with uncontrolled moderate-to-severe asthma.	Percent change from baseline to Weeks 1, 4, 8, 12, 16, 20, and 24 in concentration of FeNO. Change from baseline to Weeks 4, 8, 12, 16, 20, and 24 in exploratory biomarkers measured in nasal lining fluid. Change from baseline to Week 16 in mRNA nasal transcriptome.

Table 4 Objectives and Endpoints

Objective	Endpoint

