7 DISCONTINUATION OF STUDY INTERVENTION AND PARTICIPANT DISCONTINUATION/WITHDRAWAL

7.1 Discontinuation of Study Intervention

It may be necessary for a participant to permanently discontinue (definitive discontinuation) study intervention. Note that discontinuation from study intervention is NOT the same thing as a withdrawal from the study.

An individual participant will not receive any further study intervention if any of the following occur in the participant in question:

- 1 Withdrawal of consent to further treatment with study intervention.
- 2 Lost to follow-up.
- 3 Any anaphylactic reaction to study intervention requiring epinephrine administration.
- 4 Any SAE of \geq Grade 4 severity (see Appendix B 2).

- 5 Any SAE that is in the Cardiac Disorders system organ class.
- 6 Confirmed diagnosis of new onset of heart failure and/or progression of heart failure during the study, regardless of severity. For a participant with a suspected new onset of heart failure and/or progression of heart failure, the participant will discontinue and should not be administered study intervention unless and until agreed by the investigator and medical monitor that study intervention may continue to be administered until the diagnosis is confirmed or refuted.
- 7 Any other AE that, in the opinion of the investigator or the sponsor, warrants discontinuation of further dosing of study intervention.
- 8 Pregnancy.
- 9 Following randomisation, the participant meets ≥ 1 of the exclusion criteria (Section 5.2) or fails to meet all of the inclusion criteria (Section 5.1) for study participation, unless the PI and medical monitor agree the participant may continue receiving study intervention.
- 10 The participant misses  consecutive doses.
- 11 Following randomisation, receipt of prohibited medication (Section 6.5.4).

If study intervention is permanently discontinued, the participant will remain in the study to be evaluated for assessments at end of treatment and during follow-up, including follow-up of any AEs unless consent is withdrawn from further study participation, the participant is lost to follow-up, or the participant is enrolled in another clinical study.

See the SOA (Table 2) for data to be collected at the time of E/D and follow-up, and for any further evaluations that need to be completed.

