7.2 Participant Withdrawal from the Study

- A participant may withdraw from the study at any time at his/her own request, or may be withdrawn at any time at the discretion of the investigator for safety, behavioural, compliance, or administrative reasons. This is expected to be uncommon.
- A participant who considers withdrawing from the study must be informed by the investigator about modified follow-up options (eg, telephone contact, a contact with a relative or treating physician, or information from medical records).
- At the time of withdrawal from the study, if possible, an E/D visit should be conducted, as shown in the SOA (Table 2). See SOA for data to be collected at the time of study withdrawal and follow-up and for any further evaluations that need to be completed.

- The participant will discontinue the study intervention and be withdrawn from the study at that time.
- If the participant withdraws consent for disclosure of future information, the sponsor may retain and continue to use any data collected before such a withdrawal of consent.
- If a participant withdraws from the study, it should be confirmed if he/she still agrees for existing samples to be used in line with the original consent. If he/she requests withdrawal of consent for use of samples, destruction of any samples taken and not tested should be carried in line with what was stated in the ICF and local regulation. The investigator must document the decision on use of existing samples in the site study records and inform the Global Study Team.

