Table 9 Analysis visit windows for PGI-BR, SARS-Cov-2 serology testing, sST2 (serum), nasal mucosal sampling (mRNA), at-home cough monitoring and cough VAS

Protocol Visit	Week	Analysis Visit	Scheduled Study Day	Visit Window for Analysis (Days)
SV4	Week 0	Baseline	1	All assessments prior to the first administration of investigational product
SV10	Week 16	Week 16	113	All assessments on or after the first administration of investigational product

SV = Study Visit.

Table 10 Analysis visit windows for echocardiogram

Protocol Visit	Week	Analysis Visit	Scheduled Study Day	Visit Window for Analysis (Days)
SV4	Week 0	Baseline	1	All assessments prior to the first administration of investigational product
SV9	Week 12	Week 12	85	All assessments on or after the first administration of investigational product

SV = Study Visit.

Table 11 Analysis visit windows for EDN (plasma)

Protocol Visit	Week	Analysis Visit	Scheduled Study Day	Visit Window for Analysis (Days)
SV4	Week 0	Baseline	1	All assessments prior to the first administration of investigational product
SV7	Week 4	Week 4	29	All assessments on or after the first administration of investigational product to Day 71
SV10	Week 16	Week 16	113	72 to 141
SV12	Week 24	Week 24	169	≥142

SV = Study Visit.

Table 12 Analysis visit windows for nasal mucosal sampling (lining fluid)

Protocol Visit	Week	Analysis Visit	Scheduled Study Day	Visit Window for Analysis (Days)
SV4	Week 0	Baseline	1	All assessments prior to the first administration of investigational product

Protocol Visit	Week	Analysis Visit	Scheduled Study Day	Visit Window for Analysis (Days)
SV7	Week 4	Week 4	29	All assessments on or after the first administration of investigational product to Day 43
SV8	Week 8	Week 8	57	44 to 71
SV9	Week 12	Week 12	85	72 to 99
SV10	Week 16	Week 16	113	100 to 127
SV11	Week 20	Week 20	141	128 to 155
SV12	Week 24	Week 24	169	≥ 156

SV = Study Visit.

Daily at-home eDiary (e.g., PEF, pre-BD FEV1, FEV1, rescue medication usage, asthma symptom score, awakenings) will primarily be summarised and analysed as 2-weekly averages, separately. The assessment period of visit windows are defined in the below table.

Table 1 Labelling of 2-weekly periods

2-weekly period	Adjusted defined windows visit	Scheduled day
Baseline: as defined in Section 3.1.1	Baseline	1
Period 1: Evening of Day 1 – Morning of Day 15	Week 2	15
Period 2: Evening of Day 15 – Morning of Day 29	Week 4	29
Period 3: Evening of Day 29 – Morning of Day 43	Week 6	43

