Number and percent of participants remaining on treatment, discontinued treatment but still in study, and participants withdrawn from the study at each scheduled visit will be summarised. Participants completing the study will be listed.

Number and percentage of participants in sub-study will be summarised for the ITT population.

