4.2.6.4 Analysis of PGI-BR

The results of the 5-item questionnaire of the PGI-BR will be descriptively summarised at Week 16 by treatment group for the ITT population.

PGI-BR responses will be also reported in listing.

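### PGI-BR is scheduled only at SV10 and not at the E/D visit, so participants who withdraw from the study before SV10 give no response and the Week 16 summary labelled ITT may be selective

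*SAP*

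**What the plan says.** Protocol Section 3 (Table 4) sets an exploratory objective on the benefit-risk profile as participants perceive it, with one endpoint: "PGI-BR at Week 16". SAP 3.6.5 describes a five-item questionnaire on the participant's "perception of the overall benefits and risks of treatment at SV10". Side effects and the overall weighing of benefit against harm are among the items.

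In Protocol Table 2 the PGI-BR row has a single mark, under SV10. The E/D cell is empty, whereas ACQ-6, SGRQ and the optional feedback questionnaire are marked there. The table's footnotes define the column: "E/D = early study intervention discontinuation".

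Two groups are treated differently:

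- **Stopped dosing, still in the study.** Protocol 7.1 says "the participant will remain in the study to be evaluated for assessments at end of treatment and during follow-up", except where consent is withdrawn, contact is lost or the participant joins another study.
- **Withdrawn from the study.** Protocol 7.2 says "At the time of withdrawal from the study, if possible, an E/D visit should be conducted".

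The analysis is one sentence in SAP 4.2.6.4: the "PGI-BR will be descriptively summarised at Week 16 by treatment group for the ITT population". No missing-data rule or denominator is given for it.

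**The concern.** The endpoint asks participants whether benefit outweighed harm. People who withdraw because of side effects or lack of benefit are the ones whose answer might differ most, and the schedule does not put the question to them at the visit where they could give it.

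The protocol recognises this mechanism elsewhere. For the optional genetic sample (Section 8.6) it prefers early collection because later sampling could miss people who withdraw after an adverse event.

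The SAP has no counterweight for PGI-BR. The ACQ-6 and SGRQ responder endpoints count missing as non-response (SAP 3.4.3, 3.4.4). For PGI-BR, absent participants simply do not appear, although the table carries the ITT label. What is at stake is how one exploratory, descriptive table is read.

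**Working it through.** **1. Who has no response?** The documents give no expected PGI-BR result, withdrawal rate or power for this endpoint, so there is no planned figure to reproduce. The passages settle who is affected.

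| Participant | Visit available | PGI-BR collected? |
|---|---|---|
| Completes dosing and attends SV10 | SV10 | Yes |
| Stops dosing, stays in the study, attends SV10 | E/D, then SV10 | Yes, at SV10 |
| Withdraws from the study before SV10 | E/D, if possible | No |
| Lost to follow-up before SV10 | None | No |
| Still in the study but misses SV10 | None at Week 16 | No |

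Protocol 7.1 does not name SV10 in the second row. However, the primary estimand uses data up to Week 16 regardless of treatment discontinuation (Protocol 9.4.2.1). The SAP also counts, at each scheduled visit, participants who "discontinued treatment but still in study" (SAP 4.2.1). SV10 is therefore open to them.

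**2. Could the SAP use an E/D response?** Yes. SAP Table 9 (Section 3.1.4) assigns every PGI-BR on or after first dose to Week 16, and the same section brings E/D and unscheduled visits into the windows. Only the collection is missing.

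**3. How large could the distortion be?** Let d be the share not asked, p_s the proportion favourable among those asked and p_l the proportion favourable among those not asked.

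- Reported proportion = p_s
- Proportion for everyone = (1 − d) × p_s + d × p_l
- Distortion = d × (p_s − p_l)

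Because p_s and p_l lie between 0 and 1, the distortion lies between −d and +d.

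All inputs below are assumptions: p_s = 70%, d from 5% to 20%, and p_l varied. Splitting responses into favourable or not is also for illustration; the SAP defines no such split. Entries are percentage points, and positive means the reported figure is too favourable.

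| d | p_l = 90% | p_l = 70% | p_l = 50% | p_l = 0% |
|---|---|---|---|---|
| 5% | −1.0 | 0.0 | +1.0 | +3.5 |
| 10% | −2.0 | 0.0 | +2.0 | +7.0 |
| 15% | −3.0 | 0.0 | +3.0 | +10.5 |
| 20% | −4.0 | 0.0 | +4.0 | +14.0 |

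Example: 0.10 × (0.70 − 0.50) = 0.02, or 2.0 points.

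**4. Comparison between arms.** The distortion in a difference is the active-arm value minus the placebo value. With p_s = 70% and p_l = 50% in both arms, and 10% not asked on active against 5% on placebo, it is 2.0 − 1.0 = +1.0 point in favour of active. Swapping the two shares gives −1.0. The sign depends on which arm loses more people and why.

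**5. The 5% in the sample-size section.** Protocol 9.2 goes from 216 to 228 (216/0.95 = 227.4; 72/0.95 = 75.8, hence 76 per arm). That 5% is for participants ineligible for the primary analysis. It is neither a withdrawal rate nor a PGI-BR missingness rate, so it cannot be used to size this problem.

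**The case against.** The strongest reply is that the endpoint is defined at Week 16 and is analysed there. An E/D answer may follow a single dose, so pooling it with Week 16 answers changes what is summarised. That stands, and it is why an SV10-only summary should be kept alongside.

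Second, a reader might infer that everyone who stops early is never asked. The documents do not support this: Protocol 7.1 keeps those who only stop dosing in the study. The gap is narrower, and Protocol 7.2 expects withdrawal to be uncommon.

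Third, the SAP reports withdrawals with reasons, status at each visit, and adverse events leading to discontinuation or withdrawal, by arm (SAP 4.2.1, 4.2.7.1). A careful reader could see who is absent. This helps, but it does not supply their answers or put the number of responders on the PGI-BR table.

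Fourth, other assessments, such as SNOT-22 and oscillometry, are also unmarked at E/D, and the feedback questionnaire that is marked is not study data (Protocol 8.1.8.7). So a blank E/D cell is not unusual. Neither of those assessments, though, asks about perceived harm.

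**Conclusion.** The gap in collection is real: participants who withdraw from the study before SV10 contribute no PGI-BR response, and the ITT label on the Week 16 summary does not show this.

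A reader might go further and conclude that the reported benefit-risk perception is too favourable. That is plausible if people leave because of side effects or lack of benefit, but it is not shown. With no withdrawal rate, reasons or expected responses in the documents, the distortion may be zero or run the other way. All that can be said without assumptions is that it cannot exceed the share not asked.

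The endpoint is exploratory, descriptive and untested, so no primary or secondary conclusion depends on it. This is a cheap improvement and does not put the trial's findings in doubt.

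**What to change.** - **Protocol Table 2:** mark PGI-BR in the E/D column for participants leaving the study before SV10.
- **SAP 3.6.5 and 4.2.6.4:** name both sources. Use the SV10 response where there is one and otherwise the E/D response, which SAP Table 9 already assigns to Week 16.
- **Table 14.2.11:** show, per arm, the number of responses from each source and the number of responders out of ITT. Give an SV10-only summary alongside.

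The cost is five items at a visit already planned where possible, plus a few SAP lines. There are two limits: E/D answers reflect a shorter time on treatment, and participants lost to follow-up are still not reached. If collection can no longer be changed, reporting responders out of ITT per arm, with reasons for missing responses, is still worth doing.

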3.6.6 Asthma related inflammatory blood biomarkers

Asthma related inflammatory blood biomarkers will be assessed at visits SV1, SV4, SV7, SV8, SV9, SV10, SV11, SV12 and E/D and will include following parameters:

- plasma EDN
- total IgE
- sST2
- Allergen-specific IgE

3.6.7 Sino-nasal Outcome Test-22 (SNOT-22)

The SNOT-22 is a condition-specific health-related quality of life assessment, which captures participant-reported physical problems, functional limitations, and emotional consequences of sino-nasal conditions (Hopkins et al 2009; Piccirillo et al 2002). The SNOT-22 contains a list of 22 symptoms and social/emotional consequences of a participant's nasal disorder, and measures how severe each symptom is and the social/emotional consequences of symptoms over a 2-week period on a scale from 0 (no problem) to 5 (problem as bad as it can be). The total score is the sum of item scores and has a range from 0 to 110 (higher scores indicate poorer outcomes).

The SNOT-22 will be administered to participants who have comorbid chronic inflammatory conditions of the nasal mucosa and/or paranasal sinuses (CRS) on the eDiary according to the SoA of the CSP. The exploratory endpoint will be the change from baseline through Week 16 in SNOT-22.

3.7 Derivation of exploratory cough sub-study variables

Objective cough measurements

Objective cough frequency over 24 hours will be measured using an ACM (VitaloJAK™; Vitalograph, Buckinghamshire, UK) which will be fitted and worn by the participants for approximately 24 hours after the visits SV2 and SV10. The digitally recorded data will be sent to Vitalograph who will undertake cough counting for all participants using a standardised process. Following parameters will be provided:

- Daily cough frequency.
- Awake time cough frequency.
- Night-time cough frequency.

All frequency data will be recorded to two decimal places. The minimum recording time for the measurement to be 'done' is 1 hour, however the minimum recording time required for analysis is 18 hours within the 24-hour interval, and subjects' data with recording time < 18 hours will be excluded from analysis.

Cough VAS

Participants will be asked to complete a cough severity VAS (100 mm linear scale marked with a horizontal line by the participant, with 0 mm representing "no cough" and 100 mm representing "worst cough") measuring subjective assessment by the participant of the prior 24 hours for severity of cough symptoms (Smith et al 2006). Exploratory endpoint will be the change from baseline to Week 16 in cough VAS.

